The optional genetic sampling will be taken from subjects who have signed a separate consent form for genetic analysis on Study Day 1 prior to dose administration (Period I only). Blood samples for the determination of AZD6140, and its metabolite AR-C124910XX, in plasma will be collected on Study Days 1, 2, 3 and 4 in each treatment. Refer to Table 2 , Table 3 and Sections 4.3 and 4.4 for the timing and detailed descriptions of all the study procedures and assessments to be performed in each treatment.

If a subject experiences a spontaneous dyspnea episode any time throughout the inpatient study period (beginning with first dose administration), specific study procedures need to be completed sequentially as described in Table 3. These procedures should be completed at the onset of each dyspnea episode with the exception of an occurrence during cycle exercise testing.

If a dyspnea episode manifests intermittent symptoms within short time intervals (hours), generally if symptoms are similar and no initial abnormalities are observed on assessments, repeat assessments may be performed as needed at the investigator's judgement to monitor the subject's condition. Other diagnostic studies, such as echocardiogram or chest x-ray, may be performed to evaluate dyspnea at the investigator's discretion.

If a dyspnea episode subjectively worsens, assessments should be repeated at the investigator's discretion. The subject's dyspnea should resolve, or return to subject's baseline, before subject proceeds on to Period II (see Section 3.3.5.1).

Subjects will be discharged from the study center on Study Day 5 , after the completion of all protocol-driven procedures and assessments and at the discretion of the investigator. At discharge, subjects will be reminded of the study restrictions listed in Section 3.3.4 and instructed when to return for admission to Period II.

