3.3.5 Discontinuation of subjects from treatment or assessment

3.3.5.1 Criteria for discontinuation

Subjects may be discontinued from study treatment and assessments at any time. Specific reasons for discontinuing a subject from this study are:

- Voluntary discontinuation by the subject, who are at any time free to discontinue their participation in the study without prejudice to further treatment
- Safety reasons as judged by the investigator and/or AstraZeneca including moderate to severe dyspnea that does not resolve or return to subject's baseline within 2 weeks.
- Severe non-compliance to protocol as judged by the investigator and/or AstraZeneca.
- Incorrect enrollment (ie, the subject does not meet the required inclusion/exclusion criteria) or randomization (ie, the subject is not allocated study drug as described in the protocol) of the subject.
- Subject lost to follow-up
- A suspected/manifested infection according to WHO risk categories 2, 3, and 4 (Refer to Appendix D).

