3.4.3 Method of assigning subjects to treatment groups

Written informed consent will be obtained before enrollment and the volunteers identified with an enrollment number starting with E0001001. Subjects fulfilling the eligibility criteria will be assigned subject numbers starting with either number **101** (Cohort A), **201** (Cohort B) or **301** (Cohort C).

Using the AZ Global Randomization system (Grand) by AstraZeneca LP, volunteers treatment will be allocated as generated by the system.

Cohort	Volunteer Type	Randomization Number
A	Healthy Volunteers	101, 102, 103, 104, etc.
B	Mild Asthma	201, 202, 203, 204, etc.
C	Mild COPD	301, 302, 303, 304, etc.

Subjects will be randomized strictly sequentially within their Cohort as subjects are eligible for randomization on Day 1 of Period I before study drug administration. If a subject should be incorrectly randomized, randomization should continue with no attempt to correct the error. If a subject discontinues from the study, the randomization number will not be re-used and the subject will not be allowed to re-enter the study. Subjects who withdraw after having received study medication may be replaced by a subject who will be assigned to the same treatment sequence.

Each treatment group will consist of the same combination of matching active and placebo tablets. There will be four additional individual drug packages supplied for each cohort in the event of misrandomization, early withdrawal, etc. These will be used only as back-up and not for over enrolling subjects.

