6.4.2 Description of analysis sets

6.4.2.1 Pharmacodynamic analysis set

All subjects who have evaluable respiratory measurements in both periods of the study without any protocol deviations/violations deemed to affect the pharmacodynamics of AZD6140 will be included in the summaries and listings of the pharmacodynamic data.

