6.4.2.2 Pharmacokinetic analysis set

All subjects who have evaluable pharmacokinetic data without any protocol deviations/violations deemed to effect the pharmacokinetics of AZD6140 will be included in the summaries and listings of the pharmacokinetic data.

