6.4.3.1 Pharmacodynamic

The respiratory parameters will be descriptively summarized by treatment and listed by individual at each time point by treatment and visit for each of the cohorts using descriptive statistics. These will also be supported with graphical displays in order to ease making comparisons.

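### The both-periods rule for the pharmacodynamic set removes one-period subjects from summaries and listings: an avoidable exclusion that may depend on dyspnea

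*Protocol*

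**What the plan says.** Section 6.4.2.1 of the protocol defines the pharmacodynamic set: "All subjects who have evaluable respiratory measurements in both periods of the study", with no deviation judged to affect the pharmacodynamics, "will be included in the summaries and listings of the pharmacodynamic data". One definition thus governs both kinds of output. Section 6.4.3 rules out formal statistical analysis, and section 6.4.3.1 describes the output: "The respiratory parameters will be descriptively summarized by treatment and listed by individual at each time point by treatment and visit", within each cohort.

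The other two sets carry no such condition. The pharmacokinetic set (6.4.2.2) is "All subjects who have evaluable pharmacokinetic data without any protocol deviations/violations deemed to effect the pharmacokinetics of AZD6140". The safety set (6.4.2.3) needs only one dose.

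Several rules let a subject leave between periods. Section 3.3.5.1 lists "Voluntary discontinuation by the subject" and "Safety reasons as judged by the investigator and/or AstraZeneca including moderate to severe dyspnea that does not resolve or return to" the subject's baseline within 2 weeks. Section 3.1.2 asks that dyspnea should have cleared, or gone back to the subject's usual level, "before subject proceeds on to Period II (see Section 3.3.5.1"). Section 3.4.3 adds: "Subjects who withdraw after having received study medication may be replaced by a subject who will be assigned to the same treatment sequence". Section 3.1 plans up to 12 randomized per cohort so that at least 8 complete.

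**The concern.** The trial exists to find out what AZD6140 does to breathing, and section 3.2 says the 450 mg loading dose was picked to give dyspnea its best chance of appearing. Under 6.4.2.1, a subject who takes AZD6140 first, becomes breathless and does not return for Period II has no respiratory data in the second period. That subject leaves the pharmacodynamic outputs, listings included. The reason for leaving may be the effect under study.

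The rule is also uneven by sequence. A placebo-first subject who stops for dyspnea on AZD6140 in Period II may already have evaluable data in both periods and would then stay in.

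At stake are the measurements that Table 3 orders at each spontaneous dyspnea episode, including the blood gas, which is taken only then, and minute ventilation, which is a primary variable. With about 8 subjects per cohort, each subject is a large share of the description.

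**Working it through.** There is no planned figure to reproduce: section 6.4.4 says the sample size does not rest on a power calculation. The check follows one subject through the rules and then sizes the possible loss.

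**1. What remains for an AZD6140-first subject who does not enter Period II**

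- Adverse event: kept (6.4.2.3, 6.4.3.4).
- Respiratory rate: kept where reported as a vital sign (4.4.9.2, 6.4.3.4).
- Minute ventilation, Borg score, dyspnea index, spirometry, blood gas: section 4.3 classes all of these as pharmacodynamic, and 6.4.3.4 names none of them. Section 3.1 does use spirometry in the blinded safety review of Cohort A, but 6.4.3.4 does not carry it into the safety summaries.
- Concentration plots: 6.4.3.3 names no analysis set, so loss from them cannot be claimed.

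**2. Whether the planned output needs the rule**

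A summary by treatment, visit and time point can be computed without pairing, and a listing by individual needs none.

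**3. How likely a loss is**

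The documents give no rate of leaving between periods. Inputs are the half-life of 6 to 13 h (1.1), the minimum washout of 7 days (3.1.3), and one dyspnea discontinuation in a phase IIa study with 163 exposed to AZD6140 (3.2). The allocation ratio is not stated. I assume 1:1, so 4 AZD6140-first subjects per cohort of 8, 8 in Cohorts B and C together, and 12 overall.

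- Washout: 7 × 24 = 168 h; 168/13 = 12.9 and 168/6 = 28 half-lives. Drug-caused dyspnea lasting until Period II is unlikely.
- Rough rate: 1/163 = 0.6%. Chance of at least one loss: 1 − (162/163)^4 = 2.4% per cohort; 1 − (162/163)^8 = 4.8% in Cohorts B and C.
- Harsher rate: section 3.2 gives 5 early reporters at 400 mg and about 20% reporting overall, so at least 5/0.20 = 25 patients at that dose. If the one discontinuation came from them, the rate is at most 1/25 = 4%, and 1 − 0.96^4 = 15% per cohort.
- Purely assumed: a 20% dyspnea rate, with 10%, 25% or 50% of those affected stopping. Then 1 − 0.98^12 = 22%, 1 − 0.95^12 = 46% and 1 − 0.90^12 = 72% across all cohorts. No document supports these stopping shares.

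**4. What one loss would do, if it happened**

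Let the kept subjects have mean change m and the lost subject m + d.

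- Not replaced (7 kept instead of 8): (7m + m + d)/8 − m = d/8.
- Replaced (8 kept instead of 9): (8m + m + d)/9 − m = d/9.
- Standard error of an 8-subject mean: SD/√8 = 0.354 SD.

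| Assumed d | Shift in mean (SD) | In standard errors |
|---|---|---|
| 1 SD | 0.111 to 0.125 | 0.31 to 0.35 |
| 2 SD | 0.222 to 0.250 | 0.63 to 0.71 |
| 3 SD | 0.333 to 0.375 | 0.94 to 1.06 |

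Weighted by the chance of a loss, and taking d = 3 SD without replacement, the expected shift per cohort is 0.024 × 0.375 = 0.009 SD at the rough rate. At the harsher rate it is 0.15 × 0.375 = 0.06 SD.

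**The case against.** A both-periods set is a respectable choice in a crossover. Section 3.2 wants each subject compared with placebo. With no formal analysis, the two treatment columns are the only AZD6140 versus placebo comparison, and having the same people in both guards against between-subject differences at n of about 8. This stands: adding unpaired subjects with no paired version alongside would weaken the comparison. It does not justify removing anyone from a listing, nor does it stop a second summary being shown.

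The routes out are narrow. Section 3.3.5.1 names unresolved moderate to severe dyspnea, section 3.2 says most earlier reports were mild and cleared while dosing continued, and the washout is long. What mainly remains is voluntary withdrawal, for which no rate is given. This stands too, and it is why the point is minor.

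Replacement is optional and in itself removes no data; it slightly reduces the shift, from d/8 to d/9.

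A reader might infer that the rule understates the drug's effect on ventilation, or shrinks the contrast between patients and healthy volunteers. The documents do not support that. Section 3.2 supposes that patients may differ in how strongly they feel a change in respiratory drive, so a more breathless subject need not have a larger ventilation change. A positive d is more plausible for the Borg score and dyspnea index, which are secondary, than for minute ventilation.

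**Conclusion.** The point holds as a minor one. The protocol itself fixes a rule that can drop a subject's pharmacodynamic data for reasons tied to the effect studied, and none of the planned summaries or listings needs that exclusion.

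Losses are likely few or none: about 2.4% per cohort at the rough rate and at most about 15% at the harsher one, both borrowed from a different population and dosing regimen and both assuming 1:1 sequences. The shifts of 0.11 to 0.38 SD require both an actual loss and an assumed d. The size and direction of any bias in minute ventilation remain unknown.

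Two further stronger readings should be resisted. The rule does not hide dyspnea events, which stay in the safety set. Nor do the documents show that a loss is probable: the 22% to 72% range comes entirely from assumed stopping shares, while section 3.2 reports a single discontinuation.

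**What to change.** Amend section 6.4.2.1 so that evaluable respiratory data from every dosed period are listed and included in the by-treatment summaries, including data from subjects who do not enter Period II and are replaced. The existing condition on protocol deviations can stay.

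Show the both-periods summary beside it, labelled as the paired AZD6140 versus placebo comparison. Report the number of subjects not entering Period II because of dyspnea, by Period I treatment and cohort.

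The cost is a short change to 6.4.2.1, one extra set of descriptive tables and one count. No subjects, visits or samples are added. The all-data tables will have unequal and partly unpaired numbers per treatment, which is why the paired version should accompany them.

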6.4.2.2 Pharmacokinetic analysis set

All subjects who have evaluable pharmacokinetic data without any protocol deviations/violations deemed to effect the pharmacokinetics of AZD6140 will be included in the summaries and listings of the pharmacokinetic data.

6.4.2.3 Safety analysis set

All subjects who received at least one dose of study medication will be included in the assessment of safety.

6.4.3 Methods of statistical analyses

Statistical analysis will be carried out by Biostatistics at AstraZeneca, Wilmington, Delaware using SAS (version 8.2). Graphics to be included in the text or intended for use as supplemental figures and individual profile figures will be made using SAS or other software. Pharmacokinetic analysis will be carried out by, or under the guidance of, the Pharmacokinetic Section, Experimental Medicine, at AstraZeneca, Wilmington, Delaware.

No formal statistical analysis of the pharmacodynamic, pharmacokinetic or safety data will be done.

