Clinical Pharmacology Study Protocol

[figure not shown]
Drug Substance AZD6140
Study Code D5130C00028
Edition Number 1.0
Date

An Exploratory, Double-Blind, Randomized, Placebo-Controlled, 2-Period Crossover, 3 Cohort Pharmacokinetic/Pharmacodynamic, Single Center Study to Assess the Effect of AZD6140 on Respiratory Parameters in Healthy Subjects, Mild Asthmatics and COPD Patients Age 55 to 75 Years

The following Amendment(s) and Administrative Changes have been made to this protocol since the date of preparation:

Amendment No.	Date of Amendment
_____	_____
_____	_____

Administrative change No.	Date of Administrative Change
_____	_____
_____	_____

ASTRAZENECA PROCEDURES IN CASE OF EMERGENCY

In the case of a medical emergency you may contact the Clinical Study Team Leader. If the Clinical Study Team Leader is not available, contact the Clinical Study Team Physician at the AstraZeneca Research and Development site shown below.

Role in the study	Name	Address and Telephone number
Clinical Study Team Leader		
Clinical Study Team Physician		

For further clarifications regarding:

- Procedures in case of medical emergency see Section 8.2
- Procedures in case of overdose see Section 8.3.
- Procedures in case of pregnancy see Section 8.4 (not applicable)

PROTOCOL SYNOPSIS

An Exploratory, Double Blind, Randomized, Placebo-Controlled, 2-Period Crossover, 3 Cohort Pharmacokinetic/Pharmacodynamic, Single Center Study to Assess the Effect of AZD6140 on Respiratory Parameters in Healthy Subjects, Mild Asthmatics and COPD Patients Age 55 to 75 Years

Investigator

6

Study centre(s), type and number of subjects planned

Approximately 24 subjects (male or female of non-child bearing potential) including 8 healthy volunteers, 8 mild asthmatic patients and 8 mild chronic obstructive pulmonary disease(COPD) patients aged 55 to 75 years, inclusive, will be randomized at a single center.

Study period

Estimated date of first subject enrolled

Estimated date of last subject completed

Phase of development

Clinical Pharmacology (I)

Objectives

The primary objective of the study is to:

- Assess the effect of AZD6140 on respiratory rate and minute ventilation

The secondary objectives of the study are to:

- Assess the effect of AZD6140 on other respiratory parameters;

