The following pharmacokinetic parameters will be assessed:

Day 1: C_{max} , t_{max} , $AUC_{(0-12)}$, for AZD6140 and AR-C124910XX and the metabolite to parent C_{max} and AUC ratios.

Day 4: C_{max} , t_{max} and AUC_{τ} , for AZD6140 and AR-C124910XX, AZD6140 CL/F and the metabolite to parent C_{max} and AUC ratios.

- Pharmacodynamic

Cardiopulmonary exercise test

Minute ventilation

Spirometry (FEV_1 , FVC)

Respiratory Rate

Modified Borg Scale

Bidirectional Dyspnea Index

- Safety

Safety and tolerability will be assessed by collection of adverse events, 12-lead ECG (electrocardiogram), blood pressure, heart rate, physical examination results and laboratory assessments (chemistry, hematology, urinalysis), use of albuterol MDI.

- Genetics

Genetic analysis of the genes that are involved in absorption and disposition of, and response to AZD6140 such as the MDR-1 gene may be performed for those volunteers providing separate informed consent. The genetic samples collected from this study may be pooled with those from other studies involving AZD6140.

- Statistical methods

The respiratory parameters, and changes from baseline, will be summarized at each scheduled time point by treatment and visit for each of the cohorts using descriptive statistics. These will also be supported with graphical displays in order to ease making comparisons.

The pharmacokinetic parameters will also be descriptively summarized at each scheduled time point and treatment for the cohorts. Furthermore, graphical plots of the respiratory parameter and concentration of AZD6140 will also be explored for each of the three cohorts by visit.

Clinical Pharmacology Protocol
Study Code D5130C00028 Edition Number 1.0
Date

Safety data (adverse events, vital signs, 12-lead ECGs, laboratory data, physical examination data) will be summarized at each scheduled time point by treatment for the three cohorts using descriptive statistics.

The results of genetic analysis, if any, will be exploratory and will not be included in the clinical study report of this study.

TABLE OF CONTENTS	PAGE
TITLE PAGE.....	1
PROTOCOL SYNOPSIS.....	3
TABLE OF CONTENTS.....	7
LIST OF ABBREVIATIONS AND DEFINITION OF TERMS.....	12
1. INTRODUCTION.....	15
1.1 Background.....	15
1.2 Rationale.....	16
2. STUDY OBJECTIVES.....	17
2.1 Primary objective.....	17
2.2 Secondary objective(s).....	17
3. STUDY PLAN AND PROCEDURES.....	17
3.1 Overall study design.....	17
3.1.1 Screening/Visit 1.....	18

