2. STUDY OBJECTIVES

2.1 Primary objective

The primary objective of the study is to:

- Assess the effect of AZD6140 on respiratory rate and minute ventilation.

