2.2 Secondary objective(s)

The secondary objectives of the study are to:

- Assess the effect of AZD6140 on other respiratory parameters;
- Evaluate the pharmacokinetic/pharmacodynamic (PK/PD) relationship between AZD6140/AR-C124910XX concentrations and respiratory parameters in healthy volunteers, mild asthma patients, and mild COPD patients;
- Compare respiratory parameters between the healthy volunteers, mild asthma patients, or COPD patients;
- Compare PK of AZD6140 and AR-C124910XX in healthy volunteers, mild asthma patients, or COPD patients.
- Examine the safety and tolerability of AZD6140 in healthy volunteers compared with mild asthma patients, or mild COPD patients.

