This will be a double-blind, randomized, placebo-controlled, 2-period crossover, 3 cohort, pharmacodynamic study. Healthy volunteers are included as well as patient population (mild asthma and COPD patients) so that qualification of the differences in physiologic response and subjective experience of dyspnea can be compared to a healthy population.

Asthma and COPD patients are included primarily to ascertain if the physiologic response differs from healthy volunteers as this observation was only observed in a patient population and not in healthy volunteers in Phase I studies. Additionally, examining any dyspnea effects in COPD and asthma patients as compared to healthy volunteers will help to establish safety parameters. Healthy volunteers will be studied first to increase safety. The age range encompasses that of the Phase II study where dyspnea was first observed. Mild disease patients are chosen to minimize impact on any underlying disease state.

The primary variable will be respiratory rate and minute ventilation, based on the hypothesis of affecting adenosine receptors and preclinical observations. Cardiopulmonary exercise testing is included because provocation of the system may elicit measurable changes in physiological parameters that are not otherwise observed. Exercise testing also provides an opportunity to simulate the conditions that could contribute to dyspnea during daily activities.

A loading dose of 450 mg is chosen to maximize the potential of eliciting dyspnea. This dose will establish safety margins for a clinical loading dose that may be up to 270 mg. Dosing to 3 days will allow for attainment of steady-state plasma concentrations. Again, this will provide for assessment of dyspnea under clinically relevant conditions. A placebo crossover will be performed because dyspnea is a highly subjective sensation, and therefore comparison to a placebo baseline is desirable.

A retrospective genetic analysis to explore the genetic variables in genes that are important to absorption and disposition of, and response to AZD6140 may be carried out. Genetic sampling will be optional to all subjects enrolled. Subjects will receive the same treatment and care in the main study whether or not subjects donate a blood sample for genetic research. The genetic data from this study may be pooled with genetic results from other studies on AZD6140 to generate hypotheses to be tested in future studies.

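### A placebo crossover is run, but no within-subject AZD6140-minus-placebo difference with an interval is planned for the two primary variables

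*Protocol*

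**What the plan says.** The primary objective (Protocol 2.1) is to "Assess the effect of AZD6140 on respiratory rate and minute ventilation". A secondary objective (2.2) is to "Compare respiratory parameters between the healthy volunteers, mild asthma patients, or COPD patients". Section 3.2 gives the reason for the design: "A placebo crossover will be performed because dyspnea is a highly subjective sensation, and therefore comparison to a placebo baseline is desirable". That reason is framed around dyspnea, but the same crossover supplies the data for the two primary variables.

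Section 3.4.2 has each subject take both treatments in sequence AB or BA. Section 6.4.2.1 limits the pharmacodynamic set to subjects evaluable in both periods. The only derived pharmacodynamic variable (6.1.2) is the change from baseline within each period.

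On analysis, section 6.4.3 says: "No formal statistical analysis of the pharmacodynamic, pharmacokinetic or safety data will be done". The synopsis, under statistical methods, says that respiratory parameters and their changes from baseline "will be summarized at each scheduled time point by treatment and visit for each of the cohorts using descriptive statistics". Section 6.4.3.1 is worded differently: "The respiratory parameters will be descriptively summarized by treatment and listed by individual at each time point by treatment and visit". Section 6.4.3.3 permits, optionally, regression slopes with 95% confidence intervals against concentration. Section 6.4.4 says that the sample size rests on feasibility, and section 6.4.1 promises a SAP before database lock.

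**The concern.** The crossover and the both-periods analysis set exist so that each subject can be compared with himself or herself. Nothing in the protocol turns that pairing into an estimate with a stated precision, and the sentence in 6.4.3 discourages the SAP from adding one. The only interval mentioned anywhere is for a concentration slope, not for the randomised comparison in the primary objective. The objective of comparing cohorts has no planned contrast in the treatment effect.

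At stake is how a flat result is read. With means and standard deviations by treatment, a reader cannot tell a respiratory effect that is probably small from one estimated too loosely to exclude. Section 3.2 says that the study is to give safety data of use to later trials, so that distinction matters.

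The synopsis adds a second problem. A visit is a period (3.1.2, 3.1.4), so summarising by treatment and visit within a cohort splits it by sequence. Different people then sit in the two treatment cells of each visit.

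**Working it through.** **The plan's own figure.** The synopsis plans about 24 subjects, "including 8 healthy volunteers, 8 mild asthmatic patients and 8 mild chronic obstructive pulmonary disease(COPD) patients": 3 × 8 = 24, which agrees. No SD, correlation, effect size or power is given, so nothing else can be reproduced.

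**Cell sizes.** With 8 per cohort and two sequences, assumed 1:1 because the ratio is not stated:
- by treatment and visit (synopsis wording): 8 / 2 = 4 per cell, or 12 / 2 = 6 if all 12 allowed by section 3.1 are randomised and evaluable;
- by treatment (one reading of 6.4.3.1): 8 per cell, or up to 12.

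**Point estimate.** If the same subjects contribute at a time point in both periods, the AZD6140 mean minus the placebo mean equals the mean of the paired differences. Let π be the Period II minus Period I effect. Subjects on AB then contribute the treatment effect minus π, and subjects on BA contribute it plus π. The unadjusted mean is therefore off by π × (n_BA − n_AB) / N. This is zero at 4:4, but a quarter of π at 5:3 (2 / 8 = 0.25). Adjusting for period removes it.

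**Precision.** Units are the between-subject SD. ρ is the correlation between any two measurements in one subject and is an assumption. The t quantiles are 2.447 (6 df), 2.145 (14 df) and 2.101 (18 df).

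| Reading | 95% half-width | ρ = 0.5 | ρ = 0.7 | ρ = 0.8 |
|---|---|---|---|---|
| Raw values, unpaired, 4 v 4 | 2.447 × √(2/4) | 1.73 | 1.73 | 1.73 |
| Raw values, unpaired, 8 v 8 | 2.145 × √(2/8) | 1.07 | 1.07 | 1.07 |
| Changes from baseline, unpaired, 4 v 4 | 1.73 × √(2(1−ρ)) | 1.73 | 1.34 | 1.09 |
| Changes from baseline, unpaired, 8 v 8 | 1.07 × √(2(1−ρ)) | 1.07 | 0.83 | 0.68 |
| Paired, one cohort of 8 | 2.447 × √(2(1−ρ)/8) | 0.87 | 0.67 | 0.55 |
| Paired, 24 pooled | 2.101 × √(2(1−ρ)/24) | 0.43 | 0.33 | 0.27 |
| Difference in effect between two cohorts | 2.101 × √2 × √(2(1−ρ)/8) | 1.05 | 0.81 | 0.66 |

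For raw values over this range of ρ, the 4 v 4 reading is about 2.0 to 3.2 times as wide as the paired one, and the 8 v 8 reading about 1.2 to 2.0 times. For changes from baseline, the 8 v 8 reading is 2.145 × √2 / 2.447 = 1.24 times as wide at every ρ.

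The gain depends on ρ. At ρ = 0.3 the paired half-width is 1.02 SD against 1.07 SD, and at ρ = 0 it is 1.22 SD, so pairing then gains nothing.

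**The case against.** The study is titled exploratory, was sized on feasibility, and defers to a SAP. Descriptive analysis suits that purpose, and the absence of a hypothesis test is not an error. That stands, and no test is asked for here.

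A reader might infer that the plan throws away the within-subject comparison and reads the trial as 4 against 4 parallel subjects. The documents do not support this. The by-treatment means already give the paired point estimate, and individual listings and profile figures keep both periods visible. Changes from within-period baseline, which remove stable differences between subjects, are also summarised. Cells of 4 follow only from the synopsis wording and an assumed 1:1 split. In 6.4.3.1, visit can be read as belonging to the individual listing, which leaves 8 per cell.

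A reader might also see a contradiction between 6.4.3 and the confidence intervals in 6.4.3.3. It is weak: the regressions are optional and conditional, and the general sentence may mean only that no confirmatory testing is planned.

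The unpaired half-widths are not ones that the sponsor proposes to compute. They show only what a reader could infer from separate summaries.

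Deferral to the SAP does not settle the matter. A sentence ruling out formal analysis is a stated method, and a SAP following it literally would have no place for a period-adjusted estimate with an interval.

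**Conclusion.** The point holds as a cheap improvement. The data for a paired estimate will be collected, and the point estimate is implicit in the planned tables. Its precision, the period adjustment and the between-cohort contrast are not planned.

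The size rests on an assumed correlation, because the protocol gives none. At 0.5 to 0.8, stating the paired interval narrows what can be said from 1.07 SD (raw values, 8 v 8) to between 0.87 and 0.55 SD per cohort, and to between 0.43 and 0.27 SD pooled. Against changes from baseline the gain per cohort is modest, a factor of 1.24. Against cells of 4 it is larger, but that comparison also needs the synopsis reading and the 1:1 split.

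The cohort comparison stays imprecise even after the change, at about 1.05 to 0.66 SD. Reporting the interval makes that visible but does not cure it.

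**What to change.** - Amend 6.4.3 and 6.4.3.1, and align the synopsis, so that values and changes are summarised by treatment within cohort and listed by individual, treatment and visit.
- For respiratory rate and minute ventilation, state that the time-matched within-subject AZD6140-minus-placebo difference will be reported with a period-adjusted 95% CI, by cohort and pooled over cohorts, as an exploratory estimate without p-values.
- For the cohort objective in 2.2, report the between-cohort difference in that effect with its 95% CI, and say in advance that it will be imprecise.
- Reword the sentence in 6.4.3 to say that no confirmatory hypothesis testing is planned, which leaves room for these intervals and for the optional slopes in 6.4.3.3.

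The exact model, the handling of baseline and any averaging over time points can stay in the SAP, provided that they are fixed before unblinding. The cost is a few changed sentences and a few extra tables, with no added subjects, visits or measurements.
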